5.3.2 General Online Registration Instructions

Patients can be registered only after eligibility criteria are met.

Each individual user must have an RTOG user name and password to register patients on the RTOG web site. To get a user name and password:

- The investigator and research staff must have completed Human Subjects Training and been issued a certificate (Training is available via <http://phrp.nihtraining.com/users/login.php>).
- A representative from the institution must complete the Password Authorization Form (<http://www.rtog.org/LinkClick.aspx?fileticket=-BXerpBu5AQ%3d&tabid=219>) and fax it to [contact]. RTOG Headquarters requires 3-4 days to process requests and issue user names/passwords to institutions.

An institution can register the patient by logging onto the RTOG web site (<http://www.rtog.org>), going to "Data Center Logon" and selecting the link for new patient registrations. The system triggers a program to verify that all regulatory requirements (OHRP assurance, IRB approval) have been met by the institution. The registration screens begin by asking for the date on which the eligibility checklist was completed, the identification of the person who completed the checklist, whether the patient was found to be eligible on the basis of the checklist, and the date the study-specific informed consent form was signed.

Once the system has verified that the patient is eligible and that the institution has met regulatory requirements, it assigns a patient-specific case number. The system then moves to a screen that confirms that the patient has been successfully enrolled. This screen can be printed so that the registering site will have a copy of the registration for the patient's record. Two e-mails are generated and sent to the registering site: the Confirmation of Eligibility and the patient-specific calendar. The system creates a case file in the study's database at the DMC (Data Management Center) and generates a data submission calendar listing all data forms, images, and reports and the dates on which they are due.

If the patient is ineligible or the institution has not met regulatory requirements, the system switches to a screen that includes a brief explanation for the failure to register the patient. This screen can be printed.

Institutions can contact RTOG web support for assistance with web registration: [contact].

In the event that the RTOG web registration site is not accessible, participating sites can contact RTOG web support for assistance with web registration: [contact] or call RTOG Headquarters, at [contact], Monday through Friday, 8:30 a.m. to 5:00 p.m. ET.

6.0 RADIATION THERAPY

Note: All participating institutions will be credentialed for IMRT prior to registering patients to the study. Rapid review of cases is not required prior to patient enrollment.

Intensity Modulated Radiation Therapy (IMRT) is mandatory for this study. Image-Guided Radiation Therapy (IGRT) is mandatory when using a PTV margin of < 5 mm. Only institutions that are credentialed for head and neck IGRT are allowed to use a PTV margin of less than 5 mm.

Protocol treatment must begin within 14 calendar days after randomization.

6.1 Dose Specifications (8/5/14)

IMRT will be given in 35 fractions over 42 calendar days, which requires delivery of 6 fractions per week during 5 of the 6 treatment weeks. The sixth fraction can be delivered either on Saturday or as a second daily fraction, with at least a 6-hour interfraction interval, on one of the weekdays.

Treatment must be delivered using one single plan; concomitant boost techniques using a separate IMRT plans are not allowed. Sites must have completed pre-registration requirements for IMRT (and IGRT, if using reduced margins) credentialing prior to enrolling patients on trial.

Missed treatments due to holidays or logistic reasons can be compensated by delivering additional BID fractions, with a minimum inter-fraction interval of 6 hours, or by treating on Saturday or Sunday.

6.1.1 The primary tumor and involved nodes will be encompassed by the PTV-High Dose (PTV_7000) and will receive a dose of 70 Gy in 2 Gy fractions (see Section 6.1.3 for details of the prescription for the PTV_7000).

6.1.1.1 Regional lymph nodes that are considered to be at high risk of microscopic disease, PTV Intermediary (PTV_5950-6300), may be treated to a dose in the range of 59.5 Gy to 63 Gy in 1.7 Gy to 1.8 Gy per fraction, respectively.

6.1.1.2 Lower-risk targets, such as neck nodal levels that are not first echelon nodes and are not adjacent to levels containing grossly involved nodes, will be encompassed by PTV-Elective Dose (PTV_5600) and will receive a dose of 56 Gy in 1.6 Gy per fraction.

6.1.2 Treatment of the Low Neck

See details in Section 6.5.1. In patients with non-involved low neck nodes, the preferred technique is to treat with isocentric matching AP or AP-PA fields with a larynx block, matched to the IMRT portals just above the arytenoids. The dose will be 2 Gy per fraction prescribed to 3 cm depth to a total dose of 50 Gy in 25 daily fractions. Whole-neck IMRT is allowed.

In cases of gross involvement of the vallecula or low neck nodes, whole-neck IMRT should be considered. Whole-neck IMRT may also be considered if level VI is considered to be at high risk due to gross involvement of level IV nodes.

6.1.3 Prescription for the PTV_7000

All plans must be normalized such that 95% of the volume of the PTV_7000 is covered with prescription dose of 70 Gy.

Additionally:

- At 1 cc PTV_7000 volume on the DVH curve, the dose should not be >110% of the prescribed dose of 70 Gy.
- No volume > 0.03 cc within the PTV_7000 volume on the DVH curve should receive a dose < 95% of the prescribed dose.
- No more than 1 cc of the tissue outside the PTVs should receive \geq 105% of the prescribed dose to PTV_7000.

Dose should be reported with inhomogeneity corrections.

6.2 Technical Factors

6.2.1 Treatment Planning/Delivery

Megavoltage energy photon beam irradiation with a photon beam of > 4 MV is required. Any treatment planning and delivery system that has been credentialed for head and neck IMRT for previous RTOG trials is acceptable.

6.2.2 Image Guidance for IGRT When Using Reduced Margins

Daily image guidance of IMRT may be achieved using any one or more of the following techniques:

- Orthogonal kilovoltage (KV) images, e.g. ExacTrac;
- Linear-accelerator mounted kV and MV conebeam CT images;
- Linear-accelerator mounted MV CT images (e.g., Tomotherapy).

6.2.2.1 The institution's procedure for registering daily treatment imaging datasets with a reference dataset should comply with the following recommendations:

- Region-of-Interest (ROI) or "clip box" for fusion should be set to encompass the high dose PTV and adjacent spinal cord; if the supraclavicular region is a part of the target volume the ROI should extend to the C6 level;
- If the fusion software allows the user to create an irregular ROI (e.g. ExacTrac), treatment room objects seen on in-room x-rays should be excluded from the registration;

- Both manual (e.g. based on bony anatomy) and automatic (e.g. based on mutual information) types of registration can be used; the result of the fusion must be visually checked for the alignment of the bony anatomy, such as vertebral bodies and applicable soft tissue structures (e.g. optic nerves and/or optic chiasm).
- Following the registration, the translational and (if the appropriate technology is available) rotational corrections should be applied to the treatment couch. If all the variances are <2.5 mm (this typically corresponds to one half of the usual PRV margin), the treatment can proceed without correction (however, the physician/team may elect to perform adjustments even for a variance <2.5 mm). If one or more corrections are 2.5 to 5 mm, adjustment is necessary prior to treatment; however, re-imaging is not mandatory. If one or more of the corrections are >5 mm, the imaging must be repeated in addition to performing table/positioning adjustments. However, the use of numerous repeat IGRT studies should be avoided (see next section).

6.2.2.2 Management of Radiation Dose to the Patient from IGRT

Estimates of patient doses per imaging study for various imaging systems vary considerably. The doses are in the range of 1 mGy for Cyberknife's and BrainLab's ExacTrac planar kV-systems. The doses from helical MV CT scan on a Tomotherapy unit were estimated to be in range from 1 to 3 cGy for head and neck studies, similar to doses reported for kV cone beam CT on the Varian OBI™ and Elekta Synergy™ machine. The doses for MV cone beam CT are in the range of 10 cGy for a pelvis study to 6 cGy for a head and neck study. Thus, the doses for 3D imaging systems are in the range from 1 to 6 cGy for head and neck imaging and can contribute from 0.5 to 3% to the daily dose of 2.0 Gy. These are small enough dose contributions that if there is only one imaging study done per treatment session, the dose is not expected to have any clinical relevance to the patient. However, the imaging dose to the patient may become significant if repeated studies are done for patients with severe set up problems (e.g., requiring frequent corrections of more than 5 mm). It is recommended that patients demonstrating severe set up problems during the first 7 calendar days of treatment be moved to a treatment with larger margins.

6.3 Localization, Simulation, and Immobilization

6.3.1 Immobilization

The use of a thermoplastic head and shoulder mask is mandatory for head and neck IMRT. Patients will be planned in the supine position with their arms at their sides.

6.3.2 Planning CT scan

The treatment planning CT scan is mandatory for defining target volumes and normal organ at risk. The "planning" CT scan will be done with and without contrast, the one with no contrast is intended for use in heterogeneity corrected IMRT planning. The "structuring" scan with contrast is fused to the planning scan for the purposes of structure definition and so that the major vessels of the neck are easily visualized. An institution may elect to use the "structuring" scan as the "planning" scan. CT scan thickness should be 0.3 cm, and the CT scan should be acquired with the patient in the same position and using the same immobilization device as for treatment. All tissues receiving irradiation should be included in the CT scan limits. The scanning limits should at least encompass the orbits superiorly, and 1 cm below the supra-sternal notch inferiorly. For more accurate contouring, diagnostic CT scans and/or MRI may be fused with the planning CT scan.

6.4 Treatment Planning/Target Volumes (8/13/15)

The primary tumor and involved nodes will be encompassed by the PTV_7000 and will receive 2 Gy per fractions, while subclinical disease sites will be encompassed by PTV_5600 which will receive 1.6 Gy per fraction. The total doses will thus be 70 Gy and 56 Gy in 35 fractions, respectively. Regional lymph node areas considered to be at high risk for microscopic disease, PTV_5950-6300, may be treated to dose in the range of 59.5 - 63 Gy at 1.7-1.8 Gy per fractions.

The treatment plan used for each patient will be based on an analysis of the volumetric dose, including dose-volume histogram (DVH) analyses of the PTV (CTV with a 5 mm margin) and critical normal structures.

An "inverse" planning with computerized optimization should be used.

Structures marked “required” in the table below **must** be contoured and submitted for review. **Resubmission of data may be required if labeling of structures does not conform to the standard DICOM name as listed.**

All submitted treatment plans must strictly adhere to the structure names listed below:

GTV	Primary tumor and involved nodes Required
CTV_7000	GTV + 1cm margin Required
PTV_7000	CTV-PTV 5mm margin without IGRT; 3mm with daily IGRT Required
CTV_5600	CTV 7000 + 1cm margin and nodal regions Required when applicable
PTV_5600	CTV-PTV 5mm margin without IGRT; 3mm with daily IGRT Required when applicable
CTV_5950	Volume slightly larger than CTV 7000 Required when applicable
CTV_6000	Volume slightly larger than CTV 7000 Required when applicable
CTV_6300	Volume slightly larger than CTV 7000 Required when applicable
PTV_5950	CTV-PTV 5mm margin without IGRT;3mm with daily IGRT Required when applicable
PTV_6000	CTV-PTV 5mm margin without IGRT;3mm with daily IGRT Required when applicable
PTV_6300	CTV-PTV 5mm margin without IGRT;3mm with daily IGRT Required when applicable
SpinalCord	Spinal Cord Required
SpinalCord_05	Planning Risk Volume of 5mm Required
BrainStem	Brain Stem Required
BrainStem_05	Planning Risk Volume of 5mm Required
Parotid_L	Left Parotid Required
Parotid_R	Right Parotid Required
OralCavity	Oral Cavity Required
Lips	Lips Required
Mandible	Mandible Required
Pharynx	Uninvolved posterior pharyngeal wall plus adjacent constrictor muscles Required
Esophagus_Up	Cervical Esophagus Required
LarynxGSL	Glottic/Supraglottic (GSL) Required

Submandibula_L	Left Submandibular Salivary Gland Required
Submandibula_R	Right Submandibular Salivary Gland Required
External	External border of patient used to define Unspecified Tissue Required
PTV_7000_m08	Minimum dose(cold spot within PTV_7000 not including portion of PTV near (<8mm) skin) defined for a point that is 0.03cc in size Required
NonPTV	External minus PTVs Required

6.4.1 Gross Tumor Volume (GTV) represents the region judged to contain gross primary tumor or involved node(s) based on clinical and endoscopic examinations, CT scan, and, when applicable, other imaging techniques. Grossly positive lymph nodes are defined as any lymph nodes > 1 cm or nodes with a necrotic center.

6.4.2 Clinical Target Volume (CTV) is defined as the GTV plus areas considered at risk for containing microscopic disease delineated by the treating physician. CTV_7000 represents GTV plus a margin of generally 1 cm, and CTV_5600 represents CTV_7000 with a margin of 1 cm and nodal regions to receive elective irradiation.

When the tumor is infiltrative (endophytic) or when the border is ill defined, it might be desirable to deliver an intermediate dose (e.g. 59.5-63 Gy) to a volume (CTV_5950-6300) that is slightly larger than CTV_7000. The CTV margins can be narrower when GTV is in the proximity of the spinal cord or critical normal tissues. CTV should be limited by potential anatomical barriers to tumor spread such as air cavities and bones, and external body contours.

The guidelines for CT based delineation of lymph node levels for node negative patients can be found at the RTOG web site: <http://www.rtog.org/CoreLab/ContouringAtlases/HNAtlases.aspx>. For patients with positive neck nodes, the proposal by Gregoire (2006) for the delineation of the nodal CTV in the node-positive neck, may be used.

6.4.3 Planning Target Volume (PTV 7000, PTV 5950-6300, and PTV 5600) represents an additional margin around CTV_7000, CTV_5950-6300, and CTV_5600 to compensate for the variability of treatment set-up and internal organ motion. A minimum margin of 0.5 cm around the CTV is required in all directions to define each respective PTV, except for situations in which the CTV is adjacent to spinal cord or other critical normal tissues. In such situations, the margin can be reduced judiciously.

For those institutions using daily IGRT and that are credentialed to use IGRT for margin reduction, a minimum of 3 mm may be used for the CTV to PTV expansion. If IGRT is used without margin reduction, a minimum of 5 mm margin is required for the expansion of CTV to PTV.

When expansion of a CTV results in a PTV that extends beyond the patient's body surface, the PTV should be constrained to 5 mm from within the external contour. A 3 mm constraint of the PTV may be used if disease is near the skin surface. The use of tissue equivalent bolus material is indicated in situations where the disease is at or just under the skin surface. The PTV does not need to be constrained underneath the bolus.

6.4.4 The density corrected dose distributions shall be calculated, and the dose prescription is to be based on a dose distribution corrected for heterogeneities.

6.5 Critical Structures (8/5/14)

6.5.1 Management of the Low Neck/Supraclavicular Region (Match versus No Match)

It is recognized that comprehensive head and neck irradiation incorporating IMRT can be done in several ways, any of which is permitted for this study. Patient-specific QA measurements are required for all IMRT treatments. When a field "match" technique is used for treating the lower

neck, patient-specific measurements should include a verification of the dose coverage in the gap region for each patient.

1. **Match:** The upper cervical lymphatics and primary tumor bed are treated with IMRT. The lower cervical lymphatics and supraclavicular region are treated with a single AP (or occasionally APPA for larger patients with posterior neck at high risk) non-IMRT technique. The latter non-IMRT field(s) is matched to the upper neck IMRT fields. This technique requires comprehensive mid-line spinal cord blocking in the lower neck fields. This technique also allows for a simultaneous blocking of portions of the larynx, hypopharynx, and cervical esophagus in the lower neck fields. Matching 2 IMRT plans is allowed.
2. **No Match:** The entire clinical target volume (CTV) [upper and lower neck and primary tumor bed] is irradiated with IMRT. There is no match line between upper and lower portions of the regions at risk. In this technique, limiting radiotherapy dose to organs at risk (OARs), e.g., the cervical esophagus, is entirely achieved by inverse treatment planning via IMRT algorithms.

6.5.2 Definitions of Normal Tissues/Organs at Risk (OARs)

6.5.2.1 **Spinal Cord:** The cord begins at the cranial-cervical junction (i.e. the top of the C1 vertebral body). Superior to this is brainstem and inferior to this is cord. The inferior border of the spinal cord is at approximately T3-4 (i.e., just below the lowest slice level that has PTV on it). The spinal cord shall be defined based on the treatment planning CT scan. In addition, however, a Planning Risk Volume (PRV) spinal cord shall be defined. The PRV cord = spinal cord + 5 mm in each dimension. **This is irrespective of the use of IGRT for margin reduction.**

6.5.2.2 **Brainstem:** The inferior most portion of the brainstem is at the cranial-cervical junction where it meets the spinal cord. For the purposes of this study, the superior most portion of the brainstem is approximately at the level of the top of the posterior clinoid process. The brainstem shall be defined based on the treatment planning CT scan. In addition, however, a Planning Risk Volume (PRV) brainstem shall be defined. The PRV brainstem = brainstem + 5 mm in each dimension. **This is irrespective of the use IGRT for margin reduction.**

6.5.2.3 **Lips and Oral Cavity:** These should be contoured as 2 separate structures as the goal is to keep the lip dose much lower than the oral cavity dose. The definition of lips is self explanatory. The oral cavity will be defined as a composite structure consisting of the anterior one half to two thirds of the oral tongue/floor of mouth, buccal mucosa, and palate.

6.5.2.4 **Parotid Glands:** Parotid glands are defined based on the treatment planning CT scan.

6.5.2.5 **Pharynx:** This is defined as the “uninvolved” posterior pharyngeal wall plus adjacent constrictor muscles. This extends from the superior constrictor region (the inferior pterygoid plates level) to the cricopharyngeal inlet (posterior cricoid cartilage level).

6.5.2.6 **Cervical Esophagus:** This is defined as a tubular structure that starts at the bottom of pharynx and extends to the thoracic inlet.

6.5.2.7 **Glottic/Supraglottic Larynx (GSL):** The GSL begins just inferior to the hyoid bone and extends to the cricoid cartilage inferiorly and extends from the anterior commissure to include the arytenoids. This includes the infrahyoid but not suprahyoid epiglottis.

6.5.2.8 **Mandible:** The mandible includes the entire bony structure from TMJ through the symphysis.

6.5.2.9 **Unspecified Tissue Outside the Targets:** This tissue is located between the skull base and thoracic inlet that is not included in either the target volumes or the normal tissues described above.

6.5.3 In cases of weight loss >10%, or significant shrinkage of lymphadenopathy during therapy, it is recommended that the immobilization mask be adjusted or remade and a new plan be performed to assess the dose distributions with the current anatomy. Whether a new IMRT plan will be generated is at the discretion of the treating physician. If a new plan is made, the targets should be the same as those used for the initial plan. The new CT contour should be used for IGRT image registration with the new plan.

6.5.4 Doses to Normal Structures

6.5.4.1 **Spinal Cord:** The cord should not exceed 48 Gy to any volume in excess of 0.03 cc (approximately 3 mm x 3 mm x 3 mm). The PRV spinal cord should not exceed 50 Gy to any volume in excess of 0.03 cc. In treatment planning, the spinal cord PRV should be given the highest priority.

6.5.4.2 **Brainstem:** The PRV brainstem should not exceed 52 Gy to any volume in excess of 0.03 cc (approximately 3 mm x 3 mm x 3 mm). In treatment planning, the PRV brainstem should be

given less priority than the PRVcord but more priority than the other critical structures listed below.

- 6.5.4.3** Lips: Reduce the dose as much as possible. The mean dose should be <20 Gy.
- 6.5.4.4** Oral Cavity: Reduce the dose as much as possible. The mean dose should be <30 Gy for the non-involved oral cavity. Efforts should also be made to avoid hot spots (>60 Gy) within the non-involved oral cavity.
- 6.5.4.5** Parotid Glands: In most cases, it will be easier to spare one parotid than the other. The treatment planning goal will be for this individual parotid gland to receive a mean dose of <26 Gy.
- Contralateral submandibular gland: If contralateral level I is not a target, aim to reduce mean contralateral submandibular gland to <39 Gy.
- 6.5.4.6** Pharynx: Reduce the dose as much as possible. Some recommended (but not mandatory) treatment goals include: 1) No more than 33% of the pharynx exceeds 50 Gy; 2) Mean dose <45 Gy; 3) No more than 15% of the pharynx exceeds 60 Gy.
- 6.5.4.7** Cervical Esophagus: Reduce the dose as much as possible. Some recommended (but not mandatory) treatment goals include: Mean dose <30 Gy.
- 6.5.4.8** Glottic and Supraglottic larynx (GSL): Reduce the dose as much as possible. The glottic larynx mean dose is recommended to be <20 Gy. If whole-neck IMRT is used, under-dosage of PTV_5950-6300 and PTV_5600 adjacent to the glottic larynx will be limited to <10% receiving <95% prescribed dose.
- 6.5.4.9** Mandible: Reduce the dose as much as possible. Hot spots within the mandible should be avoided. It is recommended that maximum dose within the mandible be <66 Gy.
- 6.5.4.10** Unspecified Tissue Outside the Targets: No more than 1cc of unspecified tissue outside the targets can receive 74 Gy or more.
- 6.5.5** Prioritization of IMRT Planning
1. Spinal Cord
 2. Brainstem
 3. PTV_7000
 4. PTV_5950-6300(if applicable)
 5. PTV_5600 (if applicable)
 6. a. Pharynx
b. Parotid gland contralateral to primary tumor site
 7. a. GSL
b. Esophagus
 8. a. Lips
b. Oral Cavity
 9. a. Parotid gland ipsilateral to primary tumor site
b. Mandible
 10. Unspecified tissue outside the targets

6.6 Documentation Requirements for IMRT (9/27/12)

- Pre-treatment Radiation therapy planning CT scan (see Section 6.3.2);
- If IGRT is not used, then orthogonal images that localize the isocenter placement of IMRT are required. This information should be archived by the submitting institution, so it can be made available for possible future review.

6.7 Compliance Criteria (8/13/15)

Treatment breaks must be clearly indicated in the treatment record along with the reason(s) for the treatment break(s). Treatment breaks, if necessary, ideally should not exceed 5 treatment days at a time and 10 treatment days total. Treatment breaks should be allowed only for resolution of severe acute toxicity and/or for intercurrent illness and not for social or logistical reasons. Any treatment break(s) exceeding 2 treatment days for reasons other than toxicity/illness will be considered a protocol deviation.

All treatment plans are to be normalized to provide exactly 95% volume coverage of the PTV_7000 with 70 Gy.

	Per Protocol	Variation Acceptable	Deviation Unacceptable
Total RT dose to PTV_7000 (to 95% of the PTV)	70 Gy	66.5Gy – 73.5Gy	Outside range of Variation Acceptable
Minimum dose (“cold spot” within PTV_7000, not including portion of PTV near (< 8 mm) skin) defined for a point that is 0.03 cc in size (PTV_7000_m08)	66.5 Gy (equals 95% of prescribed dose)	< 66.5 but > 63 Gy	≤ 63 Gy
Maximum dose (“hot spot” > 1cc) within PTV_7000 NonPTV	≤ 77 Gy	> 77 but ≤ 82 Gy	> 82 Gy
Maximum dose (“hot spot” > 1cc outside the PTVs)	< 74 Gy	74-77 Gy	> 77 Gy
Total dose to PTV_5950 or PTV_6000, or PTV_6300 (to 95% of the PTV_5950 or PTV_6000, or PTV_6300)	≥ 59.5 but < 63 Gy	-----	< 59.5 or ≥ 63 Gy
Total dose to PTV_5600 (to 95% of the PTV)	56 Gy	<56 Gy but >50.4 Gy	< 50.4 Gy
Total RT dose to SpinalCord_05 (0.03 cc)	≤ 50 Gy	≥ 50 but ≤ 52 Gy	> 52 Gy
Total RT dose to BrainStem_05 (0.03cc)	≤ 52 Gy	>52 Gy but ≤54 Gy	>54 Gy
Overall RT treatment time	< 45 days	46-50 days (without a medically appropriate indication for delay)	> 50 days (without a medically appropriate indication for delay).
Non-Medically Indicated Treatment Interruptions	0-2	2-4	> 4

Recommended dose acceptance criteria for other normal tissue, but not to be used for plan score.

Structure	Recommended dose acceptance criteria
SpinalCord	D0.03cc(Gy) < 48
BrainStem	D0.03cc(Gy) < 50
Lips	Dmean(Gy) < 20
OralCavity	Dmean(Gy) < 30 Dmax(Gy) < 60
Parotid_L	Dmean(Gy) < 26
Parotid_R	Dmean(Gy) < 26
Submandibula_L	Dmean(Gy) < 39
Submandibula_R	Dmean(Gy) < 39
Pharynx	V50Gy(%) ≤ 33 Dmean(Gy) < 45 V60Gy(%) ≤ 15
Esophagus_Up	Dmean(Gy) < 30

LarynxGSL	Dmean(Gy) < 20 V66.5Gy(%) < 10
Mandible	Dmax(Gy) < 66

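### Section 6.7 scores a plan that gives the permitted 63 Gy to 95% of PTV_6300 as an unacceptable deviation

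*Combined protocol and SAP*

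**What the plan says.** Section 6.1 sets 35 fractions. Under 6.1.1.1, nodal regions at high risk of microscopic disease "may be treated to a dose in the range of 59.5 Gy to 63 Gy in 1.7 Gy to 1.8 Gy per fraction, respectively". Section 6.4 repeats that they "may be treated to dose in the range of 59.5 - 63 Gy at 1.7-1.8 Gy per fractions", and its structure table includes PTV_5950, PTV_6000 and PTV_6300. Section 6.4.2 adds that for infiltrative or ill-defined tumours it may be desirable to "deliver an intermediate dose (e.g. 59.5-63 Gy) to a volume (CTV_5950-6300) that is slightly larger than CTV_7000".

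One row of the 6.7 table covers all three intermediate PTVs and scores the dose to 95% of the volume:

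- Per Protocol: "≥ 59.5 but < 63 Gy"
- Variation Acceptable: dashes
- Deviation Unacceptable: "< 59.5 or ≥ 63 Gy"

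The PTV_7000 row, by contrast, has a Variation Acceptable range of "66.5Gy – 73.5Gy".

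Two other rows in the table matter here. Overall treatment time is Per Protocol below 45 days, and the next category is "46-50 days (without a medically appropriate indication for delay"). Non-medical interruptions are scored 0-2, 2-4 and > 4, while the text above the table states: "Any treatment break(s) exceeding 2 treatment days for reasons other than toxicity/illness will be considered a protocol deviation".

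**The concern.** The dose sections and the scoring row disagree on whether 63 Gy is allowed. The dose sections treat it as the top of the permitted range and give it a named structure. The scoring row puts it in the worst category. Because the row also names PTV_6300, a site can follow 6.1.1.1 and 6.4 exactly and be marked as having an unacceptable deviation, while a site whose coverage falls just short of its own target dose is marked compliant.

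What is at stake is the correctness of the radiotherapy quality scores assigned under 6.8. Treatment compliance is also a secondary endpoint (13.2.4). It is compared between arms with Fisher's exact test (13.6) and is one emphasis of the initial report (13.6.3). If that endpoint is built from the 6.7 scores, the reported compliance rate would be too low.

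**Working it through.** **Inputs.** 35 fractions (6.1); 1.7 to 1.8 Gy per fraction and 59.5 to 63 Gy in total (6.1.1.1, 6.4); the cut-points of the intermediate row (6.7).

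**Step 1: reproduce the permitted range.** Total dose = fractions × dose per fraction.

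- 35 × 1.7 = 59.5 Gy
- 35 × 1.8 = 63.0 Gy

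Both ends reproduce exactly, so 63 Gy is the intended top of the range and not a rounded figure.

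**Step 2: classify doses to 95% of the PTV** under the row as it stands and with the upper limit made inclusive.

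| Dose to 95% of PTV | As written | Per Protocol at ≥ 59.5 and ≤ 63 |
|---|---|---|
| 59.4 Gy | unacceptable | unacceptable |
| 59.5 Gy | per protocol | per protocol |
| 60 Gy | per protocol | per protocol |
| 62.99 Gy | per protocol | per protocol |
| 63 Gy | unacceptable | per protocol |
| 63.01 Gy | unacceptable | unacceptable |

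Only the 63 Gy line changes. As written, a PTV_6300 plan is Per Protocol from 59.5/63 = 94.4% of 63 Gy up to just under 100%, and unacceptable at 100%.

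**Step 3: room above the named level.** For PTV_6300 it is 63 − 63 = 0 Gy. For PTV_7000 the Variation Acceptable band runs 73.5 − 70 = 3.5 Gy above (3.5/70 = 5.0%). Even with the inclusive limit, 63.01 Gy stays unacceptable unless a band is added.

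**Step 4: could this be a text-extraction fault or superseded text?** The Per Protocol cell excludes 63 and the deviation cell includes it, so the two agree and one misread sign would not explain the conflict. Sections 6.4 and 6.7 carry the same date (8/13/15), so neither replaces the other.

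**Step 5: neighbouring rows.**

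- Time: below 45, then 46-50, then > 50. A course of exactly 45 days has no category.
- Interruptions: 0-2 and 2-4 both contain 2. The table accepts 3 or 4 as a variation, while the sentence above it calls non-medical breaks of more than 2 treatment days a deviation.

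**Step 6: number affected.** This cannot be computed. The documents do not say how often a 63 Gy target is used or what coverage those plans reach.

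**The case against.** The best case on the other side is that this is a slip at a single boundary value, and that much of what could be built on it does not follow. Several stronger readings are tempting.

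- **That every 63 Gy prescription is scored unacceptable.** The row scores the dose that reaches 95% of the volume, not the prescription. The explicit 95% normalisation rule applies only to PTV_7000 (6.1.3, 6.7), so a 63 Gy prescription covered at 62.9 Gy is Per Protocol. Section 6.5.4.8 also judges under-dosage of the intermediate PTV near the glottic larynx against 95% of the prescribed dose, so full prescription to 95% of the volume is not the protocol's only coverage standard. This objection stands and limits the error to plans that reach 63 Gy or more.
- **That the empty variation cell is itself an error.** The dashes are a deliberate entry, and doses above 63 Gy lie outside the permitted range, so scoring them unacceptable agrees with 6.1.1.1. Whether to tolerate slight excess is a choice for the radiation team.
- **That the lower limit is wrong too, because PTV_6300 covered at only 59.5 Gy passes.** 59.5 Gy is itself a permitted level for this region. A symmetric ±5% band would put the floor for a 59.5 Gy target at 0.95 × 59.5 = 56.5 Gy, close to the 56 Gy elective dose. Nothing in the documents shows that the present floor is wrong.
- **That cases have been mis-scored, or that the arm comparison is biased.** The documents show no scored cases, and nothing ties the choice of intermediate dose to treatment arm in this blinded trial.

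The boundary conflict itself remains: no other section resolves it.

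**Conclusion.** The inconsistency is real and minor. Followed exactly, 6.7 gives the worst score to a plan that delivers 63 Gy to 95% of PTV_6300, a dose that 6.1.1.1, 6.4 and 6.4.2 permit. The firm error lies at the upper limit only. Its practical reach is somewhat wider than one exact value, because a PTV_6300 plan that meets 63 Gy and slightly exceeds it also fails. That part depends on whether the radiation team wants a tolerance there.

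The effect is confined to radiotherapy quality scores. It extends to the compliance endpoint only on the assumption that 13.2.4 uses the 6.7 scores, which Section 13 does not state. On that assumption the compliance rate would be understated in both arms, with no expected bias between them. PFS, the significance level and the sample size are not affected. The 45-day gap and the interruption overlap are separate small faults in the same table.

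**What to change.** 1. In the intermediate-target row, make Per Protocol ≥ 59.5 and ≤ 63 Gy and Deviation Unacceptable < 59.5 or > 63 Gy. Keep the 59.5 Gy floor.
2. Ask the radiation team whether PTV_6300 should have a Variation Acceptable band above 63 Gy, as PTV_7000 has above 70 Gy. If so, start the unacceptable category above that band.
3. In the same edit, make overall time Per Protocol at ≤ 45 days, and make the interruption cells 0-2, 3-4 and > 4 treatment days. Reconcile these cells with the sentence above the table on breaks of more than 2 days.
4. Before radiotherapy compliance is reported, check the PTV_6300 cases already reviewed and rescore any that failed only on this limit.

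The cost is a few table cells and one sentence, plus a check of plans that sites already submit in DICOM format (12.2). No new data are needed. An amendment does carry site-level approval work (5.1.1). Accrual was expected to finish around March 2017 (13.5) and concurrent therapy around July 2017 (13.6.3). If few plans remain to be scored, a documented clarification to the radiation oncology co-chair who does the scoring (6.8) could serve the same purpose for the scores.
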